## 7.2 STANDARD OF CARE STUDY PROCEDURES

We will be monitoring the safety of our participants throughout the study with the following assessments. These assessments can also be found in attachments.

- i. A stimulation adverse effects questionnaire will be administered at the end of each stimulation session. This questionnaire will be used as a safety measure and to collect data on participant experience. A similar questionnaire was used in IRB #13-2995, #14-3285, and #14-1622 to evaluate ability to successfully blind using transcranial current stimulation. (*Attachment 1 and Attachment 2*).

## 7.3 LABORATORY PROCEDURES/EVALUATIONS

### 7.3.1 CLINICAL LABORATORY EVALUATIONS

During the initial session, all participants will be asked to participate in a urine drug screen in order to help screen out any individuals who have a drug use problem. A urine pregnancy test will also be performed at the beginning of the first day of stimulation for any female participant who is of child-bearing potential. A urine pregnancy test will also be performed prior to the sMRI scan, and at each maintenance sessions for women of child-bearing potential.

### 7.3.2 OTHER ASSAYS OR PROCEDURES

The Brief Assessment of Cognition in Schizophrenia (BACS) (*Attachment 6*) will be administered during the 1st day of stimulation, the 5th day of stimulation and at the final maintenance stimulation session (week 8). This assay was specifically designed to assess cognition in patients diagnosed with schizophrenia and will be used to obtain a baseline assessment of cognition in each participant. We will also be using this assay as a safety monitor and data collection tool throughout the study to assess any changes in cognition that may be seen as a result of the treatment.

There will be two procedures used throughout this study. Each participant will attend 5 consecutive weekdays of stimulation for this study. Each participant will be randomly assigned to one of four treatment-sequence groups for this study (sham or 10HZ tACS). Electrodes with a measurement of 5x5cm will be placed between Fp1 and F3 and between T3 and P3, and a return electrode, 5x7cm, will be placed over Cz. In order to detect any change(s) at the neurophysiological level, an EEG will be performed during the 1st day of stimulation, the 5th day of stimulation, and at each of the maintenance stimulation sessions. This measurement will contribute to the design of novel network-level biomarkers of schizophrenia and of treatment response. In the EEG analysis, we will employ source localization techniques to estimate the spatiotemporal dynamics of the neuronal currents in the brain. In order to reduce prediction errors and get more reliable and precise prediction, we will collect individual locations of EEG

electrodes using a digitizer(GeoScan) and structural MRI (sMRI) for each participant that is willing/able to safely complete an sMRI scan. These two additional information can help to make a well-constructed head model and source model for reconstructing location and the time-course or spectral content of a source in the brain. The electrode localization scanning using the GeoScan will be applied at each EEG recording, as there is the possibility for slight changes in electrode location at each EEG net application. As the structure of the brain will not change over the course of participation, the electrode localization for each EEG recording will be applied to the sMRI image to make the head model.

During each EEG recording, we will also be collecting ECG data. These ECG electrodes will be a part of the EEG acquisition system and will be placed on the participant's body, ideally one electrode below the right collarbone and a second one below the chest on the left. This data will be collected to look at HRV across conditions.

## 7.4 STUDY SCHEDULE

### 7.4.1 SCREENING

#### **Screening Telephone Call**

Individuals who are referred by a mental health care provider will be contacted by a researcher for an initial phone screening. Researchers will keep a Telephone Contact log for each telephone conversation with a participant throughout the study. There will be a log for each participant.

During the telephone screening, researchers will provide a brief background about Schizophrenia and tACS. Any initial questions will be answered at this point. The timeline of visits will then be explained; there will be 1 to 18 sessions, with 1 initial session, anywhere from 1 to 3 follow up screening sessions, 5 consecutive week days of daily stimulation, 1 MRI scan session, and maintenance stimulation sessions once weekly for 2 months following the initial 5 days of stimulation. The participant will be informed that compensation for their participation will be received at each session throughout the study. The participant will be asked if they have any additional questions. Once all questions have been answered, the participant will be asked if he/she is still interesting in participating in the study. If yes, the researcher will begin the initial phone screening which will determine eligibility for the initial session. The screening questions are shown below. If the required answers are given for each question, the initial session will be scheduled and a reminder call will be given at least 24 hours before initial session. We will use the approved telephone script for all telephone screenings.

### 7.4.2 ENROLLMENT/BASELINE

#### **Initial Screening Visit (Visit 1, Day 0)**

At the consent visit, participants will go over the consent form mailed to their address and all questions will be answered before they document their consent through a REDCap eConsent form. Each form will be read to the participant by the researcher, and the participant will be given the time to ask any questions about the information discussed. Each participant will be asked a series of questions (*Appendix E*) to ensure that the consent form is fully understood. Participants will physically sign both a HIPAA authorization form and the consent form to be mailed back to the researcher or brought to the first lab visit. The researcher will verify that the participant meets inclusion criteria. Next, the SCID (*Attachment 4*) will be administered in order to confirm diagnosis of schizophrenia or schizoaffective disorder and to verify that the participant does not have active alcohol or illicit drug abuse or dependency. The participant will be asked to provide verbal consent to record their SCID interview. They may

decline the recording and continue in the study. The C-SSRS (screening version) will be administered next. If a participant answers 'yes' to items 3, 4, or 5 in the suicidal ideation section in the past month or answers 'yes' to any suicidal behavior within the past six months, the study coordinator will call [name], who will determine if an acute assessment is needed. [name] will conduct this acute assessment if it is needed. Once the diagnosis has been confirmed, a baseline Auditory Hallucinations Rating Scale (AHRS) will be administered to document hallucinatory severity and frequency. Demographic information will be collected, which will include a history of medication, alcohol, and drug use. A short handedness questionnaire, a Belief about Treatments questionnaire, the BIS/BAS scale, and the HPSVQ will also be self administered via REDCap survey. The 2nd screening visit will be scheduled for approximately 2 weeks later. The participant's payment will be placed in an envelope to be mailed after the screenings are completed or distributed at the first lab visit.

#### **2nd Screening Visit (Visit 2)**

The 2nd screening visit will also take place over webex. The following questionnaires will then be administered to further check eligibility; Auditory Hallucination Rating Scale (AHRS) in order to document any change in auditory hallucination severity/frequency (*Attachment 3*). The AHRS scores from the initial screening visit and the current visit will be compared. If a change in score greater than 20% exists, then a 3rd screening visit will be scheduled for approximately 2 weeks later. If a change in AHRS score is less than or equal to 20% and eligibility has been confirmed, the week of stimulation will be scheduled. The participant's payment will be placed in the original envelope to be mailed after the screenings are completed or distributed at the first lab visit.

#### **3rd Screening Visit (Possible Visit 3)**

The 3rd screening visit will also take place over webex. The following questionnaires will then be administered to further check eligibility; Auditory Hallucination Rating Scale (AHRS) in order to document any change in auditory hallucination severity/frequency (*Attachment 3*). The AHRS scores from the 2nd screening visit and the current visit will be compared. If a change in score greater than 20% exists, then a 4th screening visit will be scheduled for approximately 2 weeks later. If a change in AHRS score is less than or equal to 20% and eligibility has been confirmed, the week of stimulation will be scheduled. The participant's payment will be placed in the original envelope to be mailed after the screenings are completed or distributed at the first lab visit.

#### **4th Screening Visit (Possible Visit 4)**

The 4th screening visit will also take place over webex. The following questionnaires will then be administered to further check eligibility; Auditory Hallucination Rating Scale (AHRS) in order to document any change in auditory hallucination severity/frequency (*Attachment 3*). The AHRS scores from the 2nd screening visit and the current visit will be compared. If a change in score greater than 20% exists, then the participant is considered not eligible to participate and will be paid for completing the session. If a change in AHRS score is less than or equal to 20% and eligibility has been confirmed, the week of stimulation will be scheduled. If the participant is considered not eligible to participate, their payment will be placed in the original envelope to be mailed. If they are eligible the payment will be added to the original envelope to be distributed at the first lab visit.

---

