In order to ensure symptom stability for each potential participant, there will be up to a 6 week period for the participant to achieve a stable AHRS score. The AHRS will be performed at 2 week intervals during screening. A stable score is defined as having less than or equal to 20% change. If the change between the first and second AHRS scores is less than or equal to 20%, then the participant will move on to the week of stimulation. If a stable score is not achieved at the second screening session, the participant will have two more opportunities at 2 week intervals during follow-up screening sessions to achieve a stable score. The participant will be paid for each session. If the participant does not achieve a stable score (if there remains a greater than 20% change in scores between consecutive AHRS administrations) by the end of the 6 weeks, the participant will not be eligible to continue participation.

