### 5.2 PARTICIPANT EXCLUSION CRITERIA

A potential participant who meets any of the following criteria will be excluded from participation in this study:

- DSM-IV diagnosis of alcohol or substance abuse (other than nicotine) within the last month or a DSM-IV diagnosis of alcohol or substance dependence (other than nicotine) within the last 3 months
- Positive urine test of cannabis, cocaine, amphetamine, barbiturates, opiates
- Current treatment (within 4 weeks) with psychotropic agents including benzodiazepines that are taken on a daily basis (limit prn use to greater than 48 hours before participating in study session)
- Medical or neurological illness (unstable cardiac disease, AIDS, malignancy, liver or renal impairment) or treatment for a medical disorder that could interfere with study participation
- History of traumatic brain injury that required subsequent cognitive rehabilitation, or cause cognitive sequelae
- A difference greater than 20% in AHRS scores between the 3rd and 4th screening visits
- Prior brain surgery
- Any brain devices/implants, including cochlear implants and aneurysm clips
- Co-morbid neurological condition (e.g. seizure disorder, brain tumor)
- Non English speakers
- Female participants who are pregnant, nursing, or unwilling to use an adequate method of contraception during study participation for those of child bearing potential
- Anything that, in the opinion of the investigator, would place the participant at increased risk or preclude the participant's likelihood of completing all components of the study

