## 5.4 PARTICIPANT WITHDRAWAL OR TERMINATION

### 5.4.1 REASONS FOR WITHDRAWAL OR TERMINATION

A study participant will be discontinued from further participation if:

- The participant has missed more than 2 non-consecutive stimulation sessions
- The participant has missed 2 consecutive stimulation sessions during the initial week of stimulation
- The participant has missed 2 consecutive weeks of stimulation during the maintenance sessions
- Any clinical adverse event (AE), laboratory abnormality, intercurrent illness or other medical condition, or situation occurs such that continued participation in the study would not be in the best interest of the participant.
- The participant meets any exclusion criteria (either newly developed or not previously recognized)
- A participant wishes to withdraw from further participation for any reason

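### At the 4th screening visit, section 7.4.2 checks AHRS stability against visit 2, while 5.2, 4.2, 5.1 and the summary point to visit 3, so eligible candidates can be turned away

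*Combined protocol and SAP*

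**What the plan says.** The 4th Screening Visit text in section 7.4.2 instructs: "The AHRS scores from the 2 nd screening visit and the current visit will be compared". The comparison and its consequence run together: the earlier score "and the current visit will be compared. If a change in score greater than 20% exists, then the participant is considered not eligible". If the change is 20% or less and eligibility is otherwise confirmed, the stimulation week is scheduled.

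Other places state the same decision differently:

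- Section 5.2 lists as an exclusion: "A difference greater than 20% in AHRS scores between the 3 rd and 4 th screening visits".
- Section 4.2 makes a candidate ineligible "if there remains a greater than 20% change in scores between consecutive AHRS administrations", with the AHRS given every two weeks during screening. At visit 4, the consecutive pair is visits 3 and 4.
- Section 5.1 requires a change of at most 20% over a two-week interval.
- The Protocol Summary compares each score with the previous one.

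The 2nd and 3rd Screening Visit texts in 7.4.2 each compare with the visit immediately before. Only the 4th-visit text skips a visit.

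**The concern.** Two operative rules govern one eligibility decision and use different data. A candidate reaches visit 4 only when visits 2 and 3 differ by more than 20%, so a visit-4 score close to one of them is usually far from the other. Conflict is therefore to be expected among the people to whom this text applies.

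The AHRS is the primary outcome, and its stability before treatment is what the rule protects. Section 10.3 says these patients are hard to recruit and plans for 40. Rejecting a candidate who meets sections 4.2, 5.1 and 5.2 wastes up to six weeks of screening and loses a recruit. Admitting one whom 5.2 excludes puts a participant with an unstable baseline into the trial.

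**Working it through.** The plan gives no figure for this rule, so there is none to reproduce. The check has three steps.

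**1. Worked examples.** Change is measured relative to the earlier score, because the documents do not define the reference.

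| Scores, visits 1–4 | Visit 1→2 | Visit 2→3 | Visit 4 vs 2 (7.4.2) | Visit 4 vs 3 (5.2, 4.2) |
|---|---|---|---|---|
| 20, 26, 20, 20 | +30.0% | −23.1% | −23.1%: not eligible | 0%: stable |
| 20, 26, 20, 26 | +30.0% | −23.1% | 0%: passes | +30.0%: excluded |

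Both candidates fail the first two checks and so reach visit 4. The verdicts do not depend on the choice of reference: 6/20 = 30% and 6/26 = 23.1% both exceed 20%.

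**2. Possible score patterns.** Section 7.1 gives 11 items scored 0–4, so totals run from 0 to 44. Take visits 2 and 3 from 1 to 44 and visit 4 from 0 to 44, and keep only patterns in which visits 2 and 3 differ by more than 20%. That leaves 70,425 patterns:

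- 11,576 pass 7.4.2 only
- 11,618 pass the visit-3 rule only
- 819 pass both
- 46,412 fail both

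Of the 24,013 that pass at least one rule, 11,576 + 11,618 = 23,194 (96.6%) get conflicting verdicts. These are counts of patterns, not probabilities.

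**3. How many candidates are affected.** The inputs from Table 2 are the variance of the AHRS difference, 5.82 (upper confidence limit 14.45), and the relation σ² = σ²_difference / [2(1 − ρ)]. The assumptions are normal scores rounded to whole numbers, equal correlation between visits, screening means of 20, 25 and 30 (not given in the documents), and ρ of 0.56 to 0.90. Table 2's note calls 0.56 plausible and conjectures 0.90.

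- ρ = 0.90: 5.82/0.20 = 29.10, SD 5.39, which reproduces Table 2.
- ρ = 0.56: 5.82/0.88 = 6.61, SD 2.57.
- Upper limit of the variance: 14.45/0.20 = 72.25, SD 8.50; 14.45/0.88 = 16.42, SD 4.05.

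Simulated screening series give:

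- about 0.2–4% of those screened reach visit 4 at variance 5.82;
- up to about 16% reach it at variance 14.45;
- the two rules disagree for roughly 44–71% of those who reach it.

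The direction of disagreement at SD 5.39 and ρ = 0.90:

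| Assumed mean | Reach visit 4 | Rejected by 7.4.2, stable against visit 3 | Pass 7.4.2, excluded by 5.2 |
|---|---|---|---|
| 20 | 3.9% | 43.8% of these | 21.9% of these |
| 25 | 1.26% | 44.5% | 16.4% |
| 30 | 0.36% | 41.6% | 12.4% |

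Per 40 people screened, the mean-20 row gives 40 × 0.039 × 0.438 = 0.68 wrong rejections and 40 × 0.039 × 0.219 = 0.34 potential wrong admissions. The mean-30 row gives 40 × 0.0036 × 0.416 = 0.06 and 40 × 0.0036 × 0.124 = 0.02. If 16% reached visit 4, that would be 6.4 of 40, with between 6.4 × 0.44 = 2.8 and 6.4 × 0.71 = 4.5 conflicting verdicts.

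**The case against.** The strongest reply is that 7.4.2 guards itself. Stimulation is scheduled only once eligibility has also been confirmed, and sections 5.1 and 5.2 must be met in full. Read together, the texts keep out the candidate with 20, 26, 20, 26. That stands, provided staff go back to 5.2 and do not treat the visit-4 comparison as the stability check. It does nothing for 20, 26, 20, 20, whom 7.4.2 declares not eligible outright.

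A second reply is that this is a copying slip. The comparison sentence is the same as in the 3rd Screening Visit text, and every other statement follows the previous-visit pattern. That is probably right, though it is an inference. It makes the repair easy, but coordinators screening a candidate will follow the procedure text as written.

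A third reply is that few people are affected. That also stands at Table 2's point estimate. A reader might reach a much higher figure, about 22% arriving at visit 4, by combining SD 5.39 with ρ = 0.56. The documents do not support that pairing: 5.39 is derived at ρ = 0.90, and the same relation gives 2.57 at ρ = 0.56.

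**Conclusion.** The inconsistency is real and sits in current, operative text. For anyone reaching the 4th screening visit, 7.4.2 can reject a candidate who satisfies 4.2, 5.1 and 5.2. It can also pass one whom 5.2 excludes, with section 5.2 itself as the only safeguard. Wrong rejection is the main consequence: in the ρ = 0.90 runs it is two to about three times as frequent as a pass that 5.2 would overturn.

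The reach is small: about 0.2–4% of those screened at the point-estimate variance, and up to about 16% at its upper limit. These figures rest on assumed screening means and on correlations taken from before and after treatment in 15 patients, not from repeated screening visits.

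A reader might infer that the slip will remove randomised patients. Section 5.4.1 discontinues a participant found to meet an exclusion that was missed, and section 10.2 analyses only completed data sets. That requires staff to overlook 5.2, randomise the patient and discover the error later. Nothing in the documents shows this to be likely, so it is a possible secondary effect. The comparison is made before allocation, so the error cannot itself depend on treatment arm. No effect on type I error or on the estimated treatment difference is shown.

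**What to change.** In the 4th Screening Visit text of section 7.4.2, change the comparator from the 2nd to the 3rd screening visit, so that it agrees with 4.2, 5.1, 5.2 and the Protocol Summary. The sponsor should confirm that this is the intent; if visit 2 was meant, those four places need amending instead. In the same amendment, state which score is the denominator of the percentage change.

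Check every existing visit-4 record against both comparisons and document any candidate whose eligibility differs. The cost is one word in the protocol and a review of what should be very few records.

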#### **7.4.3 STIMULATION WEEK**

##### **Day 1 of Stimulation (Visit 5)**

Upon participant arrival, a completed consent form and HIPAA authorization will be confirmed to be in the participant file. All participants (male and female) will be asked to complete a urine drug screening to determine eligibility for the study. Female participants will complete a urine pregnancy test to rule-out pregnancy. Vital signs

will be taken. The C-SSRS (screening version) will be administered next. If a participant answers 'yes' to items 3, 4, or 5 in the suicidal ideation section or answers 'yes' to any suicidal behavior since the initial screening visit, the study coordinator will call [name], who will determine if an acute assessment is needed. [name] will conduct this acute assessment if it is needed. Then, the AHRS (*Attachment 3*) will be administered followed by the PANSS (*Attachment 5*) and the Brief Assessment of Cognition in Schizophrenia (BACS) (*Attachment 6*). The BACS will be used as a baseline assessment of participant cognition, and will be administered again during later sessions to assess for any changes in cognitive function associated with treatment. An EEG will then be administered, with ECG data also being collected at this time. The EEG recording will include resting state data along with an auditory task, and the EEG Questionnaire will be administered.

Once the questionnaires are complete, the participant will be administered either sham or 10 Hz tACS treatment for 40-minutes. Participants will be asked to sit still and not talk during these 40-minutes, and will be asked to keep their eyes open and facing straight ahead. The *Reefscape* video will be played during the stimulation session. After each stimulation treatment, to assess any side effects of stimulation, the stimulation adverse effects questionnaire will be administered. This questionnaire will be administered at the end of each stimulation session as a safety assessment to monitor any potential side effects of the stimulation (*Attachment 1*). Participants will be paid for this visit as well as all previous screenings at the conclusion of this session.

#### **Days 2 – 4 of Stimulation (Visit 6 – 8)**

Upon participant arrival, vital signs will be taken. The participant will then receive 40-minutes of sham or 10 Hz tACS (as per the initial randomization) while sitting quietly with their eyes open. The *Reefscape* video will be played during each stimulation session. Each stimulation session will be followed by the stimulation adverse effects questionnaire. Participants will be paid at the conclusion of each session.

